The underlying causes of death will be classified as coronary [ICD-9:410-414], other heart failure [ICD-9:402, 404, 428], cerebrovascular, other vascular, cancer related, or other and unknown causes by the endpoint committee who will be blinded to treatment allocation. From an analysis viewpoint statistical censoring is only enforced at the time of death.

Investigators may be requested by the endpoint committee to provide all relevant documentation to substantiate the diagnosis of a study endpoint.

6. Safety Reporting

A summary of the organisation of reporting adverse events and endpoints is shown in the following figure:

* Rejected endpoints might potentially be SAE's.

a. Endpoints

Study endpoints are classified as:

Primary endpoints

(i) Non-fatal MI (symptomatic and silent MI) + fatal CHD

Secondary endpoints

(i) Non-fatal MI (symptomatic only) + fatal CHD

(ii) All cause mortality

(iii) Cardiovascular mortality

(iv) Fatal and non-fatal stroke

(v) Fatal and non-fatal heart failure

(vi) Total coronary endpoints = fatal CHD + non-fatal MI (symptomatic and silent) + chronic stable angina + unstable angina + fatal and non-fatal heart failure

(vii) Total cardiovascular events and procedures = cardiovascular mortality + non-fatal MI (symptomatic and silent) + unstable angina + chronic stable angina + life threatening arrhythmias + non-fatal heart failure + non-fatal stroke + peripheral arterial disease + revascularisation procedures, and retinal vascular thromboses.

Tertiary endpoints

(i) Silent MI

(ii) Unstable angina

(iii) Chronic stable angina

(iv) Peripheral arterial disease

(v) Life threatening arrhythmias (VF or sustained VT or complete heart block)

(vi) Development of diabetes mellitus

(vii) Development of renal impairment

(viii) With and without metabolic syndrome*

* As defined according to NCEP III except for replacing waist-hip ratio with BMI > 30 as patients with triglycerides ≥ 1.69 mmol/l, HDL-C for males < 1.03 mmol/l, for women < 1.29 mmol/l, BP $\geq 130/85$ mmHg, fasting glucose ≥ 6.1 mmol/l.

These events are not considered as serious adverse events.

During the study period, an event classified as an endpoint must be reported by mail to the Scandinavian Co-ordinating Centre as soon as the investigator is informed. If an investigator receives information of an endpoint that has occurred within 30 days after the study period this also has to be reported to:

[figure not shown]
Endpoint Administrator
Scandinavian Co-ordinating Centre/Ascot
Clinical Research Institute
[name]
[name]
Sweden

In the case of a patient death, a summary of available autopsy findings must be submitted as soon as possible to the Scandinavian Co-ordinating Centre. The investigator should ensure that information on such cases reported by telephone or other means and information entered in the case record forms are accurate and consistent. The endpoints are sent on a continuous basis to the Endpoint Committee for evaluation of whether they qualify for inclusion as an endpoint or not.

The Endpoint Committee, who are blinded as to study therapies, will evaluate and classify the endpoints. Confirmed endpoints will be reported back to the Scandinavian co-ordinating centre who will forward these data to the Data Safety Monitoring Committee (DSMC). Those events considered to be serious adverse events and not endpoints by the Endpoint Committee will be reported immediately to the Scandinavian Co-ordinating Centre for immediate reporting as a serious adverse event to Pfizer Clinical Research Group in the relevant country.

Endpoints will be handled as follows:

Endpoint Data Flow

b. Serious Adverse Events

Serious Adverse Events includes any experience which is not a study endpoint that suggests a significant hazard, such as events which:

- (1) are life threatening
- (2) results in a persistent or significant disability/incapacity
- (3) require inpatient hospitalisation or prolongation of a hospital stay due to other causes than endpoints (see above)
- (4) result in congenital anomaly/birth defect
- (5) require medical intervention to prevent any one of the above.(For further details please refer to the Ascot Adverse and Serious Adverse Event manual)

[figure not shown]
It should be emphasised that, regardless of the above criteria, any additional adverse experience, which the investigator considers serious, should be reported immediately.

An event classified as a Serious Adverse Event occurring during the study period or, if known by the investigator, within 30 days after the patients completion of the study, must as soon as the investigators are informed, be reported by telephone to the appropriate Pfizer Clinical Research Group office regardless of suspected relationship to study drug. (For telephone number please refer to the Ascot Adverse and Serious Adverse Event manual).

For all Serious Adverse Events, the investigator is obliged to pursue and provide information as requested by the clinical monitor in addition to that on the case record form. In general, this will include a description of the event in sufficient detail to allow for a complete medical assessment of the case and independent determination of the causality. The investigator should ensure that information on such cases reported by telephone or other means and information entered in the case record forms are accurate and consistent.

Serious Adverse Events will be handled as follows:

Serious Adverse Event Reporting Pathway

The DSMC is responsible for advising the steering committee concerning the protocol amendments or study discontinuation based on this information. The yearly safety report will not contain any information on the treatment arm, if the DSMC has not detected any safety issues. If deemed necessary by the DSMC, safety reports will be issued more frequently than the stipulated 1 year interval.

c. Non Serious Adverse Events

All ongoing Adverse Events at each visit, regardless of treatment, if not a study endpoint will be recorded on the Adverse Event Form. A follow-up of the events is required at each of the following visits until such time that the event is resolved. (For further details please refer to the ASCOT Adverse and Serious Adverse Event manual).

d. Abnormal Laboratory Test Results

The recorded results of all laboratory tests required by the protocol will be attached to the case record form. All clinically important abnormal laboratory tests occurring during the study will be repeated at appropriate intervals until they return either to baseline or to a level deemed acceptable by the investigator and the clinical monitor, or until a diagnosis that explains them is made. Abnormal laboratory test results that result in a change in study drug dosage should be recorded as adverse events in the case record form.

For patients randomised to atorvastatin or placebo:

Alanine transaminase (ALT) x 4 upper limit of normal (ULN) is to be checked after approximately 1 week, while $ALT > 2xULN$ but $\leq 4xULN$ is to be checked after approximately 3 weeks. If repeat $ALT > 4xULN$ then statin/placebo treatment should be stopped temporarily; whereas if > 2 but $\leq 4xULN$, ALT is to be checked again after approximately 3 weeks, with study treatment then stopped temporarily if ALT remains $> 2xULN$. After stopping study treatment temporarily, ALT is to be checked again after approximately 6 weeks and study treatment stopped permanently if still more than $1.5xULN$ (with 3 week follow up visits) until ALT reverts to normal: ie $\leq 1.5xULN$). If, on the other hand, $ALT \leq 1.5xULN$, then the allocated study treatment can be started again, with a further 2 early recall visits at 3-week intervals (at which ALT must remain $\leq 2xULN$, otherwise study treatment is to be stopped permanently).

Creatine kinase (CK): symptoms of myopathy (ie new unexplained muscle pain or weakness) accompanied by an otherwise unexplained elevation of $CK > 10xULN$ should result in the study treatment being stopped permanently (with 3-week follow up visits until CK reverts to normal: ie $\leq 3xULN$). $CK > 4xULN$ but $\leq 10xULN$ that cannot be explained (ie by some trauma, intramuscular injection, heavy exercise, recent myocardial infarction etc) is to be checked after approximately 1 week and, if repeat $CK > 4xULN$ then study treatment should be stopped temporarily. CK is to be checked again after approximately 6 weeks and study treatment stopped permanently if still $> 3xULN$. If, on the other hand, $CK \leq 3xULN$, then the allocated

study treatment can be started again, with a further 2 early recall visits at 3-week intervals (at which CK must remain $\leq 3 \times \text{ULN}$, otherwise study treatment is to be stopped permanently). A flow chart detailing the investigations to be undertaken is located in the Ascot laboratory manual.

e. Breaking the Randomisation Code: Emergency Procedures

Individual sealed envelopes including the randomisation code for each subject randomised in the lipid lowering part of the trial will be provided to the investigators. The envelopes must be stored in a secure storage facility. Only the investigator or a person appointed by the investigator will have access to the envelopes. Another set of sealed code envelopes will be kept at the co-ordinating centre in the UK and at the local Pfizer offices for emergency access and security back up to the site.

The envelopes should only be opened in the event of a medical emergency, requiring immediate identification of the therapy. The date and reason for breaking the code should be recorded and signed off by the investigator as follows:

- on the code envelope
- on the appropriate case record form

Such action immediately terminates the double-blind lipid lowering aspect of the study for that patient.

7. Discontinuation from Study Medication

The reason for a patient discontinuing study medication will be recorded in the case record form. A discontinuation occurs when an enrolled patient permanently ceases taking the study medication, regardless of the circumstances, prior to completion of the protocol. A discontinuation must be reported immediately to the appropriate co-ordinating centre if it is due to an endpoint or in the case of a serious adverse event to the local Pfizer office. It may not be necessary for a patient to stop treatment after an endpoint. The investigator will record the reason for study drug discontinuation, provide or arrange for appropriate follow-up for such patients, and document the course of the patient's condition. *The patients should, if at all possible, be followed to the end of the study despite discontinuation of the study drug* as the intention-to-treat analysis includes all patients.

Typically, subjects may discontinue study medication for the following reasons:

- a. At the request of the subject.
- b. If the investigator considers that a subject's health will be compromised due to adverse events or concomitant illness that develops after entering the study.

- c. If a subject is recognized after entry to be uncooperative or a consistent violator of protocol requirements.

For any subject who discontinues therapy before the study is completed, the investigator will:

- a. Complete the case record form including any summary sheet, indicating the date of and explanation for the early discontinuation of medication. If possible, provide an overall evaluation of safety of the assigned treatment.
- b. Encourage where appropriate the subject to re-start study medication.
- c. Arrange for alternative medical care of the discontinued subject if necessary.
- d. Follow the patient in the usual way to the end of the study despite discontinuation of the study medication.

IV C Clinical Supplies

The Sponsor will supply the investigator with adequate quantities of the following materials to permit completion of the study:

- Amlodipine 5 and 10mg tablets
- Atenolol 50 and 100mg tablets
- Perindopril 4mg tablets
- Bendroflumethiazide 1.25 and 2.5mg (with potassium) tablets
- Doxazosin GITS 4 and 8mg capsules
- Atorvastatin 10mg tablets
- Matching placebo for atorvastatin tablets

After discontinuation of the lipid-lowering arm of the trial, the sponsor will, where permitted by local rules and regulations, make atorvastatin 10mg available to the patients previously participating in this arm of the trial until the final visit of the main trial.

The investigator should maintain adequate records of the receipt and disposition of all study drugs supplied. Any unused medication will be returned to the Sponsor or designated pharmacies. The investigator shall be responsible for assuring that the study medication is stored in a cool, secure, limited access area, protected from extremes of light, temperature, and humidity (unless otherwise specified). Further details can be found in the drug handling manual.

V ADMINISTRATIVE MATTERS

V A Summary of Study Organization (Appendices III, IV, V)

- Two main co-ordinating centres:

UK and Ireland Cardiovascular Studies Unit
Dept. Clinical Pharmacology and Therapeutics
Imperial College School of Medicine at St. Mary's
Paddington
[name]
UK
[contact]
[contact]

Scandinavia Scandinavian Co-ordinating Centre/Ascot
Clinical Research Institute
[name]
[name]
Sweden
[contact]
[contact]

- Data collection:
 - 9000 patients from the UK and Ireland and 9000 patients from Scandinavia
 - standardised methods in each centre
 - logistics as per local requirements
 - transferred and handled at co-ordinating centres (either London or Gothenburg)
 - transferred between co-ordinating centres

- Randomisation:
 - separately via each co-ordinating centre using identical methods

- Laboratories:
UK and Ireland:
Biosys Clinical Ltd
Royal College of Surgeons in Ireland
[name]
Dublin 2, Ireland.

Scandinavia:
Medilab AB
[name] (visiting address: [name])
[name]
Sweden

V B Study committees

- Executive Committee: this consists of the two principal investigators, [name] (UK and Ireland) and [name] (Scandinavia) and [name] and [name].
- The International Steering Committee: this committee is co-chaired by [name] and [name]. The membership of 15 comprises: one member from each participating country (4 from UK and Ireland, 4 from Scandinavia); the two chairmen; one non-voting Pfizer representative; the 2 other members of the executive; and one non-voting senior member for each of the 2 coordinating centres. Observers may be present at meetings of this committee.
- The working group consists of 6 people, the executive plus 1 senior member from the UK co-ordinating centre and the Scandinavian Clinical Research Co-ordinator. This group should have executive mandate responsibility for day-to-day decisions. For major decisions, the working party will consult the steering committee. Observers may be present at meetings of this committee.
- A national working management group for the UK and Ireland and each of the Scandinavian countries will implement any major decisions. For Scandinavia, regional working groups will also be established.
- A Data Safety Monitoring Committee of experienced clinicians, epidemiologists and statisticians (approximately 5 people) not involved in the study will meet annually or as required.
- An endpoint committee consisting of 4 experienced clinicians will evaluate the blinded endpoints mailed/faxed to them on a running basis.
- An external auditing group will be responsible for ensuring that the participating centres are treating the two treatment groups in a similar fashion and with acceptable adherence to GCP.
- A sub-study committee will determine which sub-studies are acceptable considering the focus of the main study.

V C Monitoring of Study

The study will be monitored periodically by Pfizer CRA's in Scandinavia and by study monitors in the UK and Ireland in accordance with GCP to assess the progress of the study and adherence to the protocol. The investigator should maintain source documents such as laboratory reports, X-rays, ECG's, any consultation reports, complete history and physical examinations, etc. for review by the monitor.

V D Recording of Data

Data from patient visits will be entered using a Remote Data Entry (RDE) system. The methods used by Scandinavia and UK/Ireland differ. In Scandinavia the data is entered onto paper workbooks by the Investigator, then data-entered into the RDE system by the monitors. In the UK/Ireland, data is entered directly into the RDE system by site personnel. An explanation for the omission of any required data should appear on the appropriate page. All data recorded in the CRF will be signed by the Investigator or his/her appropriate designee.

Specific instructions and further detail can be found in the study instruction manual or the RDE/CRF SOP/manuals in each region.

A list of the normal ranges for all laboratory tests conducted will be provided for each of the two central laboratories. The methods employed for each assay should be available on request. Any change in the laboratory, its procedures, normal values, certification, etc. must be reported by the laboratory to the co-ordinating centre.

V E Statistical analyses and power considerations

1. Sample size

a. Comparison of blood pressure treatment

The sample size has been calculated based on several assumptions. Based on the experience from other trials and epidemiological data^{1-6, 24-27} the yearly rate of **non-fatal MI and fatal CHD** (later called endpoint rate) is assumed to be 2% before correction and 1.42% after adjusting for withdrawals and dilution from cross-over. (See below). The relative additional benefit of a 'contemporary' drug regimen (per protocol) is estimated to be 20%. This estimate is in part affected by the relatively large reductions in BP anticipated in this trial compared with previous trials. The cumulative non-compliance rate in BP-treatment is estimated to be 20% in 5 years. Including dilution from losses and non-compliance (cross-over) the estimated intention to treat (ITT) effect of the 'contemporary' regimen is 15-16%.

With a significance level of 5% a total sample size of 18000 is needed to get a power of 80% for the primary endpoint (nonfatal MI and fatal CHD) giving a total number of 1150 endpoints.

Dilution effect:

The dilution effect and the effect of losses and statin treatment on endpoint rate in the standard group have been calculated from a Markov model.

Endpoint rates:

The unadjusted endpoint rate (fatal CHD and nonfatal MI) has been calculated from experiences from similar trials (see figure 1, page 4).

Assumptions for blood pressure treatments

Annual endpoint-rate (%) in the control group unadjusted for losses, crossover and statin-effect	2.00
Relative effect of "contemporary" compared with "standard" BP-treatment (per protocol) (%)	20
Relative effect of BP-treatment corrected for losses and crossover Intention to Treat (ITT) %	15-16
Proportion statin treated open or randomised (%)	40-45
Treatment effect in endpoint rate by statin (ITT) 10 mg atorvastatin (%)	30
Relative reduction (%) in endpoint rate in the "blood pressure standard" group because of statin treatment effect (%)	18
Cumulative losses of endpoint during 5 year (%)	10
Cumulative cross-over from "standard" to "contemporary" (%)	20
Cumulative cross-over from "contemporary" to "standard" (%)	20
Annual endpoint-rate (%) in the "standard" BP treatment group after adjustment for #	1.42
Cumulative endpoint rate (%) during 5 years in the control group after adjustment for #	6.9
Significance level (alpha) (%) Interim analysis by safety committee will use level 0.005 leaving 0.045 for final test	5
Sample size (9000 contemporary + 9000 standard)	18000
Power (%)	80 ← lower power

losses and the dilution effect from cross-over and statin effect

b. Comparison of atorvastatin and placebo

These calculations are based on the experience from clinical trials and epidemiological data.^{9-19,28,29} It is assumed that 9000 patients (50%) will be randomised to either 10 mg atorvastatin or placebo (see section III C).

The following assumptions are made:

Cholesterol reduction with 10 mg atorvastatin (%)	30
Difference in cholesterol between 10 mg atorvastatin and placebo (mmol/l) 1.7	
Relative (%) effect on endpoint (nonfatal MI and fatal CHD) of 10 mg atorvastatin compared with placebo (40% optimally in long term studies) (ITT)	30
Power for the primary endpoint (nonfatal MI and fatal CHD) given by Cumulative endpoint rate (nonfatal MI and fatal CHD) on placebo for five years (%)	6.35
Significance level (%)	1
Sample size	9000
Power (%)	90

2. Statistical analysis

The statistical method for the main analysis will be a log rank test using time to event (nonfatal MI and fatal CHD) as the primary information. The significance level for the primary comparisons of the antihypertensive and the lipid lowering components will be 0.05, both including adjustment for interim looks (for details see section V E.1) and 0.01 for secondary and tertiary analyses. These analyses will be done without adjusting for baseline factors and will be performed according to the intention to treat principles (ITT). All analyses using 'time to particular event' will be analysed in the same way. The Cox proportional hazards model with adjustment for important prognostic variables will be done as complementary analyses.

Analyses using information on compliance with treatment (per protocol analyses) will be done as secondary analyses. To some extent these analyses are more sensitive to the rate of cross-over or discontinuation.

Main effect variables will also be analysed in certain subgroups to search for possible interactions. Such analyses will be seen as explanatory, will involve chi-square tests for interaction, and will be foundations for future hypotheses. P-values and confidence intervals will be presented for all comparisons.

The statistical analyses will be performed by the two co-ordinating centres under the supervision of the ASCOT Steering Committee. The unblinded statistical information for the Safety Committee will be provided by one specially named person at the co-ordinating centre in Gothenburg.

V F Disclosure of data and publication

All information obtained as a result of the study will be regarded as CONFIDENTIAL, at least until appropriate analysis and review by the Sponsors and investigator(s) are completed. Permission from the Executive Committee is necessary prior to disclosing any information relative to this study outside of the Steering Committee. It is proposed that the results relating to the two primary endpoints will be published separately. The results may be published or presented by the investigator(s), but the major Sponsors (Pfizer) will be provided with a complete dataset. All sponsors (Pfizer, Servier, and Lovens) will be given the opportunity to review and comment on any such results for up to 1 month before any presentations or publications are produced.

V I INVESTIGATOR'S APPROVAL

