- Fasting blood sample: total cholesterol, HDL, triglycerides, glucose, electrolytes, creatinine and, if randomised to statin/placebo, liver function tests (LFT's).
- Urine: stix for protein, blood and sugar.
- BP treatment modified if BP above target (see section IV B3).
- Changes in medication recorded.
- Study medication allocated.
- Appointment made for next visit.

g. Subsequent follow-up visit (year 1, 2, 3, 4, 5 ± 1 month)

- Body weight.
- Endpoints and adverse events recorded.
- BP and HR.
- ECG at year 2 only.
- Fasting blood sample: Hb, total cholesterol, HDL, triglycerides, glucose, electrolytes, creatinine, liver function tests (LFT's), and at year 2 only extra blood for frozen storage.
- Urine: stix for protein, blood and sugar.
- BP treatment modified if BP above target (see section IV B3).
- Changes in medication recorded.
- Study medication allocated.
- Appointment made for next visit.

h. Follow-up visit (years 1½, 2½, 3½, 4½, 5½ ± 1 month)

- Endpoints and adverse events recorded.
- BP and HR.
- Smoking and alcohol intake recorded.
- BP treatment modified if BP above target (see section IV B3).
- Study medication allocated.
- Appointment made for next visit.

i. Extra visits

In addition it may be necessary to arrange extra visits to control or monitor blood pressure or for other reasons. The timing of all visits and any extra visits should be recorded in the case record forms, including the reason for the visit and any extra laboratory tests or procedures carried out.

j. Final visit

All participating subjects should have a final assessment at the end of the study. This assessment should include:

- Endpoints and adverse events recorded.
- BP and HR.
- Body weight measurements.
- Smoking and alcohol intake recorded.
- ECG.
- Fasting blood sample for lipid profile; HB, glucose, creatinine, electrolytes and liver function tests (LFT's), and extra blood for frozen storage.
- Urinalysis with stix for microalbuminuria, protein, blood and sugar.
- Changes in medication recorded.

As one arm of the trial has been discontinued before the other, a final visit examination will be performed for the patients involved in the discontinued arm of the trial. These patients will then continue in the remaining arm of the trial until the study is finally terminated, when a final visit for that limb of the trial will also be carried out.

k. SUMMARY SCHEDULE OF EVENTS

1 2 3 4 5 6 7 8 9

MONTHS	-1	0	1.5	3	6	12	18	24	30	36	42	48	54	60†	66/ final

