Medical History And Eligibility	X	X*													
Previous Antihypertensive Medication And Side Effects	X														
Current Illness/adverse events ¹	X	X	X	X	X	X	X	X	X	X	X	X	X	X	X
Morbidity/Mortality Endpoints															
Informed Consent	X														
Withdrawal Of Antihypertensive Drugs		X													
Height■, Weight	X					X		X		X		X		X	X
BP, Heart Rate	X	X	X	X	X	X	X	X	X	X	X	X	X	X	X
ECG	X	X	X*		X*	X*		X*		X*		X*		X*	X
Blood Tests	X														
Urine Tests	X				X	X		X		X		X		X	X
Physical Examination		X													
Extra Visits Optional For Drug Up-Titration When Necessary															

- ★ bloods for electrolytes, creatinine for those randomised to receive ACE inhibitor. This sample should be taken within a few weeks of initiating an ACE inhibitor whenever this occurs during the trial
- ◆ bloods to include LFT for those randomised to receive statin/placebo
- only at screening
- † If this is the final visit see requirements for final eligibility only
- If triglyceride level is >4.5mmol/l or glucose is >7mmol/l at screening, subjects will be recalled during this period for a fasting blood sample to evaluate eligibility (see section IVB, 4. b).
- ∅ Current illness only is recorded at visit -1.
- 1

5. Central ascertainment of biochemical effects, and of cardiovascular events, cancers and cause-specific mortality

a. *Assessment of biochemical changes throughout the trial*

Two central laboratories will be used for all analyses - one in the UK and Ireland and one in Scandinavia.

b. *Ascertainment of cardio-vascular events*

The co-ordinating centre will seek additional information (including, if necessary, any pertinent hospital records) from the patient's own doctor about relevant hospital admissions, suspected myocardial infarctions, strokes, coronary angioplasty or vascular surgery which has been recorded on the case record form/worksheet. This will allow central review of any vascular events by the endpoint committee *who will be blind to treatment allocation*.

Standardised criteria for classifying diagnoses will be used by the endpoint committee. These criteria will be defined, a priori, in a manual of operations in conjunction with the endpoint committee members.

c. *Follow-up of morbidity and mortality*

[figure not shown]
The co-ordinating centre will seek the certified causes of all deaths of randomised patients. For all patients the appropriate National Registries, where available, will be used.

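### Death as the only stated censoring event leaves no cut-off for lost patients or for the closed lipid limb

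*Protocol*

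**What the plan says.** Section IV B 5 c (Follow-up of morbidity and mortality) gives the protocol's only censoring rule: "From an analysis viewpoint statistical censoring is only enforced at the time of death". Section V E 2 makes the main analysis a "log rank test using time to event (nonfatal MI and fatal CHD) as the primary information", by intention to treat, and handles all other time-to-event endpoints in the same way.

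Four other places bear on the rule:

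- The assumptions table in V E 1 a has a line "Cumulative losses of endpoint during 5 year", set at 10%.
- IV B 4 j (Final visit) states "As one arm of the trial has been discontinued before the other, a final visit examination will be performed for the patients" of the discontinued arm, and adds "These patients will then continue in the remaining arm of the trial until the study is finally terminated".
- IV C (Clinical Supplies) identifies the lipid-lowering arm as the one discontinued. It says that the sponsor will, subject to local rules, "make atorvastatin 10mg available to the patients previously participating in this arm of the trial until the final visit of the main trial".
- IV B 7 asks that patients, if at all possible, "be followed to the end of the study despite discontinuation of the study drug", because the intention-to-treat analysis includes everyone.

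No section gives a censoring rule for loss, withdrawal or the closure of a limb. The SAP is not among the documents at hand.

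**The concern.** A log-rank test needs each patient's time at risk to end when event status stops being known, or when the comparison ends. A rule that admits death alone has two consequences if applied as written.

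First, patients who are lost stay in the risk set as event-free. This understates event rates, and it distorts the hazard ratio if loss differs between the two open-label blood-pressure regimens.

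Second, lipid-limb patients go on supplying endpoint data in the blood-pressure limb after their own limb has closed. The literal rule would carry that time into the atorvastatin-placebo comparison, and into the atorvastatin-amlodipine synergy analysis (tertiary objective 3), although both groups may by then take the same drug. The lipid hazard ratio would move toward 1.

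**Working it through.** **1. The plan's own figures reproduce.** The power formula is Φ(|ln HR|·√D/2 − z), where D is the number of events and z the two-sided critical value.

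- Lipid limb (V E 1 b: 9000 patients, 6.35% placebo 5-year risk, 30% reduction, 1% level, taken as two-sided). D = 4500 × (0.0635 + 0.04445) = 486, and power at HR 0.70 is 91%, against 90% stated.
- Blood-pressure limb (V E 1 a: 15–16% effect, final test at 0.045, 80% power). At HR 0.845 the Schoenfeld formula needs 1143 events and Freedman's 1148, against 1150 stated.

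The point therefore does not rest on a sample-size error.

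**2. Lipid limb, post-closure time counted or not.** The closure date and the uptake of atorvastatin after closure are not in the protocol. They are assumptions here, as is a common closure time after randomisation with follow-up to year 5.

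- Placebo hazard: λ = −ln(1 − 0.0635)/5 = 0.0131 a year. Atorvastatin hazard: 0.70λ.
- After closure the placebo hazard falls to 0.70λ/h, where h is the assumed post-closure HR: 1.0 for full uptake, 0.85 for partial uptake.
- With D₁ events before closure and D₂ after, average ln HR = (D₁·ln 0.70 + D₂·ln h)/(D₁ + D₂).

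Example, closure at year 3 with full uptake: D₁ = 296 and D₁ + D₂ = 454, so ln HR = 296 × (−0.357)/454 = −0.2325 and HR = 0.79. Power at 1% is Φ(0.2325 × √454/2 − 2.576) = 46%. Censored at closure it is Φ(0.357 × √296/2 − 2.576) = 69%.

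Power at two-sided 1%:

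| Closure | Censored at closure (HR 0.70): events, power | Full uptake, run to year 5: events, HR, power | Partial uptake, run to year 5: events, HR, power |
|---|---|---|---|
| Year 2 | 198, 47% | 438, 0.85, 19% | 458, 0.78, 53% |
| Year 3 | 296, 69% | 454, 0.79, 46% | 468, 0.75, 69.5% |
| Year 4 | 392, 83% | 471, 0.74, 74% | 478, 0.72, 83% |

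Section V E 2 gives 0.05 for this comparison rather than 1%. At 5%, closure at year 3 with full uptake gives 70% against 87% if censored at closure.

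**3. Lost patients kept at risk.** If loss builds up evenly to a cumulative proportion L, about L/2 of the person-time is unobserved but still counted.

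- Equal 10% loss: rates are understated by about 5% (a control rate of 1.42% a year reads 1.35%), and the HR stays at 0.845.
- Illustrative loss of 12% against 8% with no true effect: HR = (1 − 0.06)/(1 − 0.04) = 0.979, favouring the arm with more loss. The shift in the test statistic is |ln 0.979| × √(1150/4) = 0.36. Against a critical value of 2.005, type I error is 5.9% instead of 4.5%.
- A wide split of 15% against 5%: HR = 0.925/0.975 = 0.949, and type I error is 13.5%.

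The protocol gives one loss figure and no split by arm, so both splits are assumptions.

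**The case against.** The strongest reply is that the sentence means something else. It sits in a paragraph on follow-up and causes of death, not in the analysis section. Read with IV B 7, it says that stopping drug or having a non-fatal event does not end follow-up, which is correct. Taken literally it would not even censor survivors at study end, so nobody could apply it literally. Cut-off dates are also commonly left to a SAP.

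Most of this stands as a reading of intent. It does not rescue the wording: the protocol fixes a rule here, and a SAP would have to follow it or contradict it. Study end is implied because data stop then. Lipid closure is not implied in the same way, because endpoint data on those patients keep arriving.

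A reader might infer that the protocol plans to count post-closure events in the lipid comparison. The documents do not support that. The discontinued limb has its own final visit with endpoints recorded, and V F proposes to publish the two primary results separately; both suggest a limb-specific end of follow-up. Neither sets an analysis cut-off.

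A reader might also infer that the blood-pressure test has an inflated type I error. That needs loss to differ between arms, which the protocol does not say. Event capture after loss would also reduce any bias: registries ("For all patients the appropriate National Registries, where available, will be used"), telephone contact and follow-up to study end are all provided for. The planned 1.42% rate already allows for losses.

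**Conclusion.** The concern holds in a limited form. The sentence is wrong as written for a log-rank analysis, and it conflicts with the protocol's own 10% losses and its closed lipid limb. Its probable intent is sound and should be kept.

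The firm consequence, if the rule were followed literally, is dilution of the lipid hazard ratio: from 0.70 to about 0.74–0.85 with full uptake after closure, or about 0.72–0.78 with partial uptake. Loss of power is not firm. It is clear with full uptake and immaterial with partial uptake. All of these figures depend on an assumed closure date and uptake.

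For lost patients, the expected effect is event rates about 5% too low. Bias in the blood-pressure hazard ratio is conditional on unequal loss. Severity is moderate, because the harm arises only under the literal reading and the text is easily corrected.

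**What to change.** Replace the sentence in IV B 5 c with:

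> Stopping study drug and non-fatal events of other types do not censor. Follow-up is censored at the earliest of death not counted in the endpoint, last contact at which clinical event and vital status were ascertained (including registry follow-up where available), and the cut-off date of the comparison. For the atorvastatin-placebo comparison and the atorvastatin-amlodipine synergy analysis the cut-off is the closure (final visit) of the lipid limb; for the blood-pressure comparison it is the end of the study.

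Add that a missing later ECG does not by itself censor clinical follow-up. Silent MI is part of the primary endpoint and is detected only by ECG. Without this line, a strict reading of last known status would discard known follow-up for symptomatic MI and CHD death. Report post-closure lipid follow-up separately, labelled as an extension.

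The cost is one paragraph; visit dates are already recorded in the case record form (IV B 2). The downside is fewer events in the main lipid comparison, for example 296 rather than 454 with closure at year 3 and full uptake.
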